8.2 Statistical Analysis Plan

Descriptive statistical analysis will be conducted for all primary and secondary endpoints, for all patients, and for subgroups (abiraterone versus no prior abiraterone and sipuleucel-T versus no prior sipuleucel-T). The proportion estimate will be reported with 95% confidence interval, and the continuous variables will be summarized using nmissing, mean, std, median, min, and max. Safety and adverse events will be presented in a tabular form.

One-sample binomial test will be used to assess whether the proportion of PSA response (PSA decrease of at least 50%) is significantly greater than 0.05. Univariable logistic regression analysis will be conducted to assess the association between immunological parameters and PSA response responses. Scale in logit will be assessed for all continuous parameters that are identified to be significantly associated with PSA response. Our hypothesis is that Microsatellite instability and PD-L1 expression together with other immunological parameters are potential predictors for PSA response. As the incidence of MSI and the presence of PD-L1 expression are relatively small (under 10% for MSI), we propose to enroll 30 additional subjects to this study to help find 1) whether MSI and PD-L1 expression are likely predictors for PSA response and 2) whether any other immunological parameters independently or jointly predicts the PSA response. Multivariable logistic regression model will be fitted to identify the potential predictors. Stepwise variable selection will be used to find the final model. Random forest will also be used as a parallel method for building the predictive model. The area under the Receiver Operating Characteristic (ROC) curve will be computed for the discrimination ability of the predictive model. 10-fold cross validation will be performed to assess the validation of the proposed model. Due to the limited sample size, we will not have a separate testing set to validate the predictive model. Therefore, all findings are exploratory and need to be validated. Kaplan-Meier curve will be plotted to illustrate the PSA progression free survival for all, and for subgroups (abiraterone versus no prior abiraterone and sipuleucel-T versus no prior sipuleucel-T).

8.3 Sample Size Computation

Patients with PSA progression on treatment are extremely unlikely to have a PSA response without a change in therapy. If 25% of subjects treated with pembrolizumab upon progression with enzalutamide have a PSA response, this therapy would be worthy of further study. Using a null hypothesis of 5% and alternate hypothesis of 25%, 25 evaluable patients are needed with 90% power and a one-sided alpha of 0.05. To account for potential drop-out, we will enroll 28 subjects.

We propose to add 30 additional subjects to this study (for a total of 58) to better evaluate the association between PSA responses and candidate risk factors (MSI and PD-L1 expression with other immunological parameters), and to build a prognostic model. The proposed sample size will achieve 80% power to detect AUC of 0.85 against AUC of 0.6 using two-sided z test at 5% significance level. We understand that it is not guaranteed that a predictive model with good predictive ability can be constructed, because both MSI and PD-L1 expressions are relatively rare. However, the collected data and analysis will be clinically valuable to help us determine whether a future larger study is worthy. . In the initial study, we did biopsies on any subject that had a

metastatic lesion that could be biopsied, but subjects were not required to have a lesion that could be biopsied. We are doing biopsies on all 30 additional patients along with the tests we did on earlier participants.

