
Pembrolizumab (previously known as SCH 900475 and MK-3475) is a potent and highly selective humanized monoclonal antibody (mAb) of the IgG4/kappa isotype designed to directly block the interaction between PD-1 and its ligands, PD-L1 and PD-L2.

Our 38th subject just completed four cycles of pembrolizumab. We have seen seven robust responses so far. The degree of response is surprising, and we do not currently understand the

mechanism. We are expanding enrolment to an additional 30 patients with enriched correlative work to help us understand which patients respond to this therapy.

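### The only power figure for the 30-patient expansion fits the combined model, not the aim of testing MSI and PD-L1 as predictors; the planned univariable logistic regression can also fail for a rare, strong marker

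*Combined protocol and SAP*

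**What the plan says.** Section 8.2 (Statistical Analysis Plan) gives rarity as the reason for adding 30 patients: "As the incidence of MSI and the presence of PD-L1 expression are relatively small (under 10% for MSI"). It sets two aims. The first is "whether MSI and PD-L1 expression are likely predictors for PSA response"; the second is whether other immunological parameters predict response, alone or jointly. No prevalence or cut-off is given for PD-L1.

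The planned methods in 8.2 are univariable logistic regression of immunological parameters on PSA response, then a multivariable model with stepwise selection and a parallel random forest. The AUC is to be computed for the resulting predictive model.

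Section 8.3 names both evaluating the association of MSI, PD-L1 and other parameters with response and building a prognostic model as purposes of the added patients. It supports the total of 58 with one statement: "The proposed sample size will achieve 80% power to detect AUC of 0.85 against AUC of 0.6 using two-sided z test at 5% significance level". The numbers of responders and non-responders behind this are not stated, and neither power nor precision is given for the association of either marker with response.

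**The concern.** The question that motivates the expansion concerns two uncommon markers, where the null is no association. The power statement concerns something else: whether a score's AUC exceeds 0.6 when it is truly 0.85. A rare yes/no marker misses most responders even when every carrier responds, so its AUC has a low ceiling. A reader of 8.3 could take the 80% as assurance about MSI and PD-L1 that it does not give.

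The analysis that does address the first aim has its own weakness. In a 2x2 table with few carriers, the most striking result (all carriers respond) makes the odds ratio estimate infinite and the usual Wald test uninformative. Section 8.3 intends these data to help decide whether a larger study is worthwhile, so a strong MSI signal reported as non-significant would matter.

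**Working it through.** **Inputs from the document.** N = 58; AUC 0.85 against 0.60; two-sided 5% (8.3). MSI prevalence under 10% (8.2). Design response rate 25%: "Using a null hypothesis of 5% and alternate hypothesis of 25%, 25 evaluable patients are needed with 90% power" (8.3). Section 4.1.1 reports "We have seen seven robust responses so far" when the 38th subject had completed four cycles: 7/38 = 18.4%, exact 95% CI 7.7% to 34.3%. That section does not say these are confirmed 50% PSA declines, so 18.4% is an assumption for the endpoint. Expected responders among 58 are 0.25 × 58 = 14.5, or 0.184 × 58 = 10.7.

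**Step 1: reproduce the 80%.** With n1 responders and n0 = 58 − n1 non-responders, the Hanley-McNeil variance is [A(1−A) + (n1−1)(U−A²) + (n0−1)(V−A²)]/(n1·n0), where U = A/(2−A) and V = 2A²/(1+A). For n1 = 12, the SE is 0.0956 at A = 0.60 and 0.0731 at A = 0.85. Power = Φ[(0.25 − 1.96 × 0.0956)/0.0731] = Φ(0.857) = 80.4%. Other splits give 76.9% (11 responders), 85.9% (14) and 88.0% (15). The stated figure is therefore reasonable for a score that can reach 0.85.

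**Step 2: AUC ceiling for a binary marker.** Let the marker have prevalence m and the overall response rate be p, with m ≤ p. If every carrier responds, sensitivity is m/p and specificity is 1, so AUC_max = 0.5 + m/(2p).

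- m = 10%, p = 25%: 0.5 + 0.10/0.50 = 0.70.
- m = 10%, p = 18.4%: 0.5 + 0.10/0.368 = 0.77.
- m = 5%: 0.60 and 0.64 respectively.

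An AUC of 0.85 needs m/p ≥ 0.70: prevalence of at least 17.5% at p = 25%, or 12.9% at p = 18.4%. At m = 10% it needs p ≤ 0.10/0.70 = 14.3%, which lies inside the CI for 7/38.

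**Step 3: power of the planned association test.** Assumptions: N = 58 all assayed, 20% overall response (between the document's two rates), MSI prevalence 9%, and a Wald test, since 8.2 does not name the test. If a proportion c of carriers respond, non-carriers respond at (0.20 − 0.09c)/0.91. All tables were enumerated with a random number of carriers; separated tables count as non-significant for Wald.

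| Carriers responding | Non-carriers responding | Wald | Fisher exact |
|---|---|---|---|
| 100% | 12% | about 0% | 97% |
| 80% | 14% | 52% | 82% |
| 50% | 17% | 32% | 33% |

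The table separates in over 99% of trials in the first row. In the second row, all observed carriers respond or all fail in about 35%.

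**Step 4: how far Fisher's test goes.** At 5% prevalence and 20% overall response, its power is 75%, 52% and about 17% when 100%, 80% and 50% of carriers respond. At the document's own rates (18.4% and 25%) and 10% prevalence, it is 97-98% if all carriers respond and 25-42% if half do. With an assumed 45 patients assayed, 9% prevalence with 80% of carriers responding falls from 82% to 71%, and 5% with all responding from 75% to 60%.

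**The case against.** The strongest reply is that the plan never tests MSI or PD-L1 singly against an AUC of 0.6. Section 8.2 attaches the AUC to the predictive model, and 8.3 lists the markers together with other immunological parameters. A model with other parameters is not bound by the ceiling in Step 2. The first aim already has a no-association analysis in the univariable logistic regression, which reads as covering both markers. Section 8.3 concedes that a good model is not guaranteed because both markers are rare, and 8.2 calls all findings exploratory.

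Most of this stands. A reader might infer that the 80% is wrong, or that a perfect MSI marker would be declared a failure for missing an AUC threshold. The document supports neither: the figure reproduces, and no such rule exists. A reader might also infer that no marker below 10% prevalence can ever reach 0.85. That is too absolute, because a response rate of 14.3% or less would allow it at 10% prevalence. Nor can the ceiling be carried over to PD-L1, which has no stated prevalence and might be analysed as a graded score. Two non-overlapping markers at an assumed 10% each could reach 0.5 + 0.20/0.50 = 0.90 at 25% response.

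The reply does not supply a power or precision figure for the first aim, and the caveats do not say that the 80% leaves the single markers uncovered. It also leaves the separation problem in place.

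**Conclusion.** The concern holds in a limited form. The 80% in 8.3 is sound for a combined model with about 12 responders, but it is not power for whether MSI and PD-L1 predict response, and no other figure is offered for that aim. For MSI alone, the powered alternative is out of reach at both response rates in the document (ceilings 0.70 and 0.77), provided the true rate exceeds about 14.3%. For PD-L1 this is not shown.

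The practical loss lies in the planned regression, if it is read by a Wald test: for a strong, rare marker, power falls to about 0% or 52% where Fisher's test has 97% or 82%. For a moderate effect the two are alike and both weak (32% and 33%), so it would be wrong to infer that a 2x2 table answers the marker question well in general. These powers rest on assumed prevalence, overall response, carrier response rates and complete assay data. Section 8.3 itself notes that earlier patients were not required to have a lesion that could be biopsied.

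**What to change.** In 8.2, for MSI, and for PD-L1 if it is dichotomised at a pre-stated cut-off, replace the Wald-based univariable logistic regression with response proportions in carriers and non-carriers, exact 95% confidence intervals and Fisher's exact test.

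In 8.3, state that the 80% applies to the combined multi-marker model and give the assumed number of responders (12 reproduces it). Add Fisher power for the marker associations over a range of carrier counts (for example 3, 5 and 8 of 58) and carrier response rates. Include weaker effects and fewer than 58 assayed patients.

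The cost is a few sentences and one table, with no added patients, samples or visits. The downside is that the 80% no longer appears to cover the single markers, and the restated power depends on assumed carrier counts and is low for moderate effects.

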9.0 LABELING, PACKAGING, STORAGE AND RETURN OF CLINICAL SUPPLIES

9.1 Investigational Product

The investigator shall take responsibility for and shall take all steps to maintain appropriate records and ensure appropriate supply, storage, handling, distribution and usage of investigational product in accordance with the protocol and any applicable laws and regulations.

Clinical Supplies will be provided by Merck as summarized in Table 10.

Table 10 Product Descriptions

Product Name & Potency	Dosage Form
Pembrolizumab 100 mg/ 4mL	Solution for Injection

9.2 Packaging and Labeling Information

Clinical supplies will be affixed with a clinical label in accordance with regulatory requirements.

9.3 Clinical Supplies Disclosure

This trial is open-label; therefore, the subject, the trial site personnel, the Sponsor and/or designee are not blinded to treatment. Drug identity (name, strength) is included in the label text; random code/disclosure envelopes or lists are not provided.

9.4 Storage and Handling Requirements

Clinical supplies must be stored in a secure, limited-access location under the storage conditions specified on the label.

Receipt and dispensing of trial medication must be recorded by an authorized person at the trial site.

Clinical supplies may not be used for any purpose other than that stated in the protocol.

9.5 Returns and Reconciliation

The investigator is responsible for keeping accurate records of the clinical supplies received from Merck or designee, the amount dispensed to and returned by the subjects and the amount remaining at the conclusion of the trial.

Upon completion or termination of the study, all unused and/or partially used investigational product will be destroyed at the site per institutional policy. It is the Investigator's responsibility to arrange for disposal of all empty containers, provided that procedures for proper disposal have been established according to applicable federal, state, local and institutional guidelines and procedures, and provided that appropriate records of disposal are kept.

10.0 ADMINISTRATIVE AND REGULATORY DETAILS

10.1 Confidentiality

Patient confidentiality will be protected by keeping all hard copies in a locked file cabinet or in a locked room, on a protected floor that only allows access to those with the appropriate badge. Any information stored on a computer will be behind the OHSU firewall. HIPAA procedures will also be followed.

10.2 Compliance with Financial Disclosure Requirements

Funds given to investigators will be reported via the Sunshine Act by Merck.

10.3 Compliance with Law, Audit and Debarment

This trial will be conducted in compliance with all applicable institutional, local, and federal regulations. This includes auditing by appropriate regulatory authorities if necessary.

10.4 Compliance with Trial Registration and Results Posting Requirements

Under the terms of the Food and Drug Administration Modernization Act (FDAMA) and the Food and Drug Administration Amendments Act (FDAAA), the Sponsor of the trial is solely responsible for determining whether the trial and its results are subject to the requirements for submission to the Clinical Trials Data Bank, <http://www.clinicaltrials.gov>. Information posted will allow subjects to identify potentially appropriate trials for their disease conditions and pursue participation by calling a central contact number for further information on appropriate trial locations and trial site contact information.

10.5 Quality Management System

OHSU Knight Cancer Institute, through the auditing function of the Knight Clinical Trials Office, is responsible for ensuring that all member investigators and affiliate investigators conduct clinical research studies in compliance with local IRB standards, FDA regulations and NIH policies and in accordance with the Data and Safety Monitoring Plan policies and procedures <http://ozone.ohsu.edu/cancer/sharedres/kctoresdocs.cfm>

Locally initiated studies will be audited by OHSU Knight CI Auditor. Newly approved studies may be audited anytime after enrollment has been initiated. Each OHSU Knight approved treatment protocol will be audited on an annual basis in accordance with the Knight Data and Safety Monitoring Plan.

It is the responsibility of each participating site's principal investigator to ensure that the study is conducted in compliance with local IRB standards, FDA regulations, and NIH policies. It is also the responsibility of each site's principal investigator to ensure that quality assurance audits at their site are conducted according to their institution's policies and procedures. The quality assurance audit process provides assurance that reported data accurately reflects the data in the primary subject record.

10.6 Data Management

The Sponsor will be responsible for developing data collection tools such as Case Report Forms (CRF), Study Management Tools, and a database if appropriate. Data required to meet the objectives of this protocol will be collected via CRF and transmitted in a secure fashion. A Study-Specific Data Monitoring Plan (SsDMP) will be developed as a separate document for both the Lead Site and any participating Sub-sites. Risk based monitoring will be utilized, with remote monitoring of source documentation and protocol compliance. At the discretion of the Sponsor, monitoring or auditing in addition to that outlined in the SsDMP may be conducted.

10.7 Inclusion of Women, Children and Minorities

No OHSU Knight Cancer Institute study will focus on any particular racial or ethnic subset. No subject will be excluded from the study on the basis of racial or ethnic origin. Male and minority volunteers will be recruited for this study from the general population and 100% men will be studied.

The racial and ethnic composition of the study should represent that of the state of Oregon (see Table 11). If the prevalence of the disease being studied is consistent across race, ethnicity and gender, then these figures can be used to calculate projected enrollments in Table 12. If the disease being studied does *not* affect both genders or all races and ethnicities equally (e.g., cervical cancer only affects women and Black males are more likely than White males to have prostate cancer), then this information should be taken into account when calculating the projected enrollment. The OHSU General Clinical Research Center has links to various sources of statistics on their webpage at www.ohsu.edu/gcrc. If a different source is used in calculating projected enrollments, that source should be cited below Table 2.

Table 11: Population Demographics - Oregon (%)

Ethnic Category	Sex/Gender		
	Females	Males	Total
Hispanic or Latino			11.7
Not Hispanic or Latino			88.3

Ethnic Category	Sex/Gender		
	Females	Males	Total
Ethnic Category: Total of all subjects*			100*
Racial Category			
American Indian or Alaskan Native			1.4
Asian			3.7
Black or African American			1.8
Native Hawaiian or other Pacific Islander			0.3
White			83.6
More than one race			3.8
Unknown/Other			5.3
Racial Category: Total of all subjects*			100*
TOTALS	50.4	49.6	100*

Source: U.S. Census Bureau, 2010 *Totals may not equal 100 due to rounding.

Table 12: Projected Accrual for the Present Study

Ethnic Category	Sex/Gender			
	Females	Males	Unknown	Total
Hispanic or Latino	0	2	0	
Not Hispanic or Latino	0	26	0	
Unknown	0	0	0	
Ethnic Category: Total of all subjects*	0	28	0	28*
Racial Category				

Ethnic Category	Sex/Gender			
	Females	Males	Unknown	Total
American Indian or Alaskan Native	0	0-1	0	
Asian	0	0-1	0	
Black or African American	0	0-1	0	
Native Hawaiian or other Pacific Islander	0	0-1	0	
White	0	26	0	
More than one race	0	0-1	0	
Unknown	0	0-2	0	
Racial Category: Total of all subjects*	0	28	0	28*

Source: Adapted from U.S. Census Bureau, 2010 *Totals may not equal 100 due to rounding.

This protocol does not include children for the following reason: Prostate cancer does not affect children under the age of 18.

12.0 APPENDICES

12.1 ECOG Performance Status

Grade	Description
0	Normal activity. Fully active, able to carry on all pre-disease performance without restriction.
1	Symptoms, but ambulatory. Restricted in physically strenuous activity, but ambulatory and able to carry out work of a light or sedentary nature (e.g., light housework, office work).
2	In bed <50% of the time. Ambulatory and capable of all self-care, but unable to carry out any work activities. Up and about more than 50% of waking hours.
3	In bed >50% of the time. Capable of only limited self-care, confined to bed or chair more than 50% of waking hours.
4	100% bedridden. Completely disabled. Cannot carry on any self-care. Totally confined to bed or chair.
5	Dead.

* As published in Am. J. Clin. Oncol.: *Oken, M.M., Creech, R.H., Tormey, D.C., Horton, J., Davis, T.E., McFadden, E.T., Carbone, P.P.: Toxicity And Response Criteria Of The Eastern Cooperative Oncology Group. Am J Clin Oncol 5:649-655, 1982.* The Eastern Cooperative Oncology Group, Robert Comis M.D., Group Chair.

12.2 Common Terminology Criteria for Adverse Events V4.0 (CTCAE)

The descriptions and grading scales found in the revised NCI Common Terminology Criteria for Adverse Events (CTCAE) version 4.0 will be utilized for adverse event reporting. (<http://ctep.cancer.gov/reporting/ctc.html>)

12.3 Response Evaluation Criteria in Solid Tumors (RECIST) 1.1 Criteria for Evaluating Response in Solid Tumors

RECIST version 1.1* will be used in this study for assessment of tumor response. While either CT or MRI may be utilized, as per RECIST 1.1, CT is the preferred imaging technique in this study.

* As published in the European Journal of Cancer:

E.A. Eisenhauer, P. Therasse, J. Bogaerts, L.H. Schwartz, D. Sargent, R. Ford, J. Dancey, S. Arbuck, S. Gwyther, M. Mooney, L. Rubinstein, L. Shankar, L. Dodd, R. Kaplan, D. Lacombe,

J. Verweij. New response evaluation criteria in solid tumors: Revised RECIST guideline (version 1.1). Eur J Cancer. 2009 Jan;45(2):228-47.

In addition, volumetric analysis will be explored by central review for response assessment.

12.4 Correlative Work –Contact study sponsor for information regarding collection, processing, and shipping of blood and tissue.

12.5 Biopsy of Metastatic Lesion

Due to the nature of metastatic prostate cancer, most biopsies will be from bone. This biopsy is being done for the correlative endpoints (see section 4.2.3.2). Bone biopsies present unique challenges with respect to the collection and processing. However, regardless of collection technique, rapid freezing of the biopsy material is critical to subsequent success. As part of the trial, we will provide kits to each site enrolling patients so as to facilitate a standardized collection of tissue.

Patients are positioned by radiology and conscious sedation may be administered to improve patient comfort. This is based on the judgment of the interventional radiologist and may be restricted in some centers due to the availability of supportive services.

During the image-guided biopsy procedure we recommend the following general rules when choosing a metastatic site and a specific location within the metastatic tumor for biopsy:

- 1) If the patient has bone only disease, the pelvis is the preferred site for biopsy.
- 2) Any biopsy kit capable of obtaining core biopsies from bone is acceptable. The Bonopto Coaxial biopsy system with eccentric drill (<http://www.vasocare.co.kr/product04-5.html>) is a recommended system. Internal diameter is 1.3mm. This is the smallest for collection of usable material.
- 3) In the bone, extremely blastic lesions seldom yield usable material. Yields are greater if biopsies are performed in marrow of abnormal signal intensity directly adjacent to blastic lesions. Often, we pass the needle tangential to the blastic lesion in the marrow space for our most successful collections.
- 4) In soft tissue, do not biopsy from regions of metastatic lesions that appear necrotic on CT or MRI due to extremely poor yield.
- 5) It is important that excessive compressive force is not required or used to expel the biopsy from the biopsy needle. This obscures cellular morphology. If it is difficult to expel the biopsy from the core needle, alternative biopsy kits should be used.

Please follow the directions below when processing the biopsy material:

Required Materials

Included in Kit:

- Disposable cryo-molds 15x15x5mm
- Sakura Tissue-Tek OCT compound
- Metal plate or tray

- Sarstedt black permanent marker
- Tissue-Tek Mega-Cassettes
- Styrofoam cooler
- Container of neutral buffered formalin (2 provided, keep extra, an additional vial will be included with the new box)

*Keep all remaining materials after procedure is completed for use on future biopsies unless otherwise noted

Not Included (should be available on site)

- Dry Ice (pellet form, smaller pellet size works best)
- Syringe needle (core manipulation; ≤19g)
- Forceps (fine toothed)

Protocol for Biopsies

1. Prepare a cold working surface by filling the supplied styrofoam cooler container roughly half full of dry ice. Shake the container to form a fairly even layer.
2. Place the metal sheet or tray into the cooler and allow it to cool below -10°C. Temperatures below this point will freeze OCT compound quickly, facilitating the block formation. Having a flat metallic surface is also important.
3. Prior to heading to the collection, place several cryomolds on the cold metal surface allowing them to cool down prior to the biopsy.
4. Label 5 tissue cassettes, then place on dry ice to pre-chill before use during the procedure.
5. Take the cooler setup to the location of the biopsy and be sure to have easy access to it during the procedure. Be sure to take the formalin vial in the zip-lock bag as well.
6. Once the radiologist says a core is about ready, fill one of the cryomold trays roughly half-full of OCT so that the compound is partially frozen by the time the core is added. The OCT compound will appear opaque as it solidifies.
7. Transfer a core to the partially solidified OCT layer in the cryomold. The best method of tissue transfer from the biopsy needle to the pallet will depend on the type of needle used. The core biopsy can be directly placed into the cryomold of OCT, but care must be taken to ensure the core is lying as close to flat as possible as it freezes. Bonopty and other hollow core needles will yield a cylindrical core that is ejected via a plunger needle. The pressure created by the plunger directly onto the core can unpredictably eject the core from the needle. If the core cannot be placed directly on the OCT, it can be ejected onto a gauze pad and transferred immediately onto the OCT so as to minimize time for RNA degradation and protein de-phosphorylation. This helps to maintain needle sterility and allows for more careful manipulation of the core away from the sterile procedure cart. Manipulation of the core from gauze pad to cryomold is done with a syringe needle.
8. Positioning of the core is very important. Be sure to place the core flat down on the center of the OCT layer. The tissue can freeze on contact if the OCT layer has solidified, thus preventing manipulation once the tissue is on the OCT surface. Adding the core to OCT prior to solidification is ideal since the tissue and OCT will then freeze at the same time, resulting in better sectioning later. Layers frozen in different stages tend to cause separation during sectioning.

9. Immediately cover the core with OCT, working in a slow circular motion around the core such that OCT fills in the sides, then surrounds the top. Contact of the liquid OCT with the tissue core is important to preserve the tissue and facilitate in cryo sectioning later.
10. Once the OCT becomes opaque in each cryomold, the tissue block is ready to be transferred to the labeled cold cassette.
11. In addition to collecting fresh-frozen biopsy cores, 2 core must be collected for paraffin embedding. This core should be placed in the container of neutral buffered formalin. Close the jar tightly, and return to the zip-lock bag.
12. Package the biopsies into the provided insulated box. The cold cryo cassettes should be placed in dry ice in the insulated section of the box, and the formalin vial contained within the zip-lock bag should be placed outside of the insulated region of the box. The appropriate spot for the formalin vial will be labeled.
13. Include with the shipment, the sample shipment log that should include comments regarding core quality (long cylindrical core, bone shards, mostly blood clot, etc), the quantity of cores and any irregularities in the freezing process. The technician performing the collection should be sure to note their unique patient ID, the biopsy date, and the time of the procedure as well.
14. Prior to any shipments, the study coordinator and designated laboratory staff at OHSU must be notified. Notification should come in the form of email at least 2 – 3 days or, if possible, a week prior to an anticipated shipment. The email should consist of the date of scheduled biopsy, unique patient ID, participating site name and site contact; this should be sent to Specimen Manager.
15. Mail by Express Overnight delivery to the address specified on the provided shipping labels. Unless special arrangements are made, do not ship on Fridays, Saturdays, or Sundays.

